5.2.3 PROCEDURAL SUCCESS ENDPOINT

Procedural Success will be assessed at 1 month and is defined as:

- Device Success, and
- None of the following device or procedure related SAEs:
 - Life threatening bleeding
 - Major vascular or cardiac structural complications requiring intervention
 - Pericardial effusion requiring drainage or surgery (includes tamponade)
 - Stage 2 or 3 acute kidney injury (includes new dialysis)
 - Severe heart failure or hypotension requiring IV inotrope, ultrafiltration or mechanical circulatory support
 - Prolonged intubation > 48 hours

5.2.4 CLINICAL OUTCOMES

Clinical Outcomes will be assessed at 1 month, 6 months & annually and are defined as:

- Re-hospitalization rates for the underlying condition (heart failure)
- Re-intervention rates for the underlying condition (tricuspid regurgitation)
- Change in Tricuspid Regurgitation (assessment made by change in EROA) from baseline
- Change in peripheral edema as assessed by subject weight loss (kilograms) from baseline
- Change in NYHA Class from baseline
- Change in 6 minute walk test distance (meters) from baseline
- Change in Quality of Life as assessed by the SF-12 and KCCQ questionnaires from baseline

6 STUDY DESIGN

This is a multi-center (≤ 12), international, prospective, single arm, safety study designed to assess the safety and device performance of the FORMA System.

A total of seventy-eight (78) subjects will be enrolled in the study. All enrolled study subjects will be assessed for clinical follow-up at the following intervals: 1 month, 6 months, 1 year and annually for 3 years post implant procedure. Centers that do not have experience with the investigational device will be allowed a single “roll-in” subject to become familiar with the study device and procedure.

A description of each study visit and required study procedures are included in Section 8.0, Procedures and Methods. In addition, a summary of required procedures is listed in Table 10.

7 SUBJECT POPULATION

7.1 DEMOGRAPHIC AND CLINICAL CHARACTERISTICS

This clinical study is for adult subjects with clinically significant, symptomatic, tricuspid regurgitation who are at high surgical risk for standard tricuspid repair or replacement as assessed by the Heart Team.

All subjects who meet the initial study eligibility requirements will be evaluated for study participation.

Candidates for this study must meet all of the following inclusion criteria and none of the exclusion criteria:

7.2 INCLUSION CRITERIA

The Investigator has the responsibility of screening potential subjects to determine if the patients meet all the inclusion criteria. The following are requirements for entry into the study:

1. Signed and dated EC approved study consent form prior to study related procedures
2. Eighteen years of age or older
3. Clinically significant, symptomatic (NYHA Functional Class II or greater), tricuspid regurgitation (Stage D per 2014 AHA/ACC guidelines) requiring tricuspid valve repair or replacement as assessed by the Heart Team
4. Functional tricuspid regurgitation (e.g., EROA \geq 0.4 cm² or equivalent guideline directed value) as the primary etiology
5. NYHA Functional Class II or greater or signs of persistent right heart failure despite optimal medical therapy
6. Determined by the 'HEART Team' (a minimum of one Cardiologist, and one Cardiac Surgeon) to be at high surgical risk for tricuspid valve repair or replacement and the benefit-risk analysis supports utilization of the investigational device
7. Willing to attend study follow-up assessments for up to 3 years

7.3 EXCLUSION CRITERIA

The Investigator at the study site must exclude subjects if any of the exclusion criteria are present. The following are the criteria for exclusion from participating in the clinical study:

1. Tricuspid valve/right heart anatomy not suitable for the study device:
 - a. Native tricuspid annulus area $< 2.14 \text{ cm}^2$ (9 mm device), $< 2.63 \text{ cm}^2$ (12 mm device) or $< 3.27 \text{ cm}^2$ (15 mm device) as measured by transthoracic echocardiography or computed tomography
 - b. Sub-valvular structures/anatomy that would preclude from proper anchor or Spacer placement, positioning and retrieval
2. Access pathway vessel diameter less than 7.1 mm (9, 12 and 15 mm devices)
Moderate or greater tricuspid valve stenosis
3. Untreated clinically significant coronary artery disease requiring immediate revascularization
4. Any therapeutic invasive cardiac procedure performed within 30 days of the scheduled implant procedure
5. Patients not already receiving dialysis with renal insufficiency (eGFR < 25) per lab test ≤ 48 hours prior to scheduled implant procedure
6. Myocardial infarction within 30 days of scheduled implant procedure
7. Hemodynamic instability within 30 days of scheduled implant procedure
8. Patient requiring surgery under general anesthesia for any reason within 30 days of scheduled implant procedure
9. Severe left ventricular dysfunction with ejection fraction $< 25\%$ within 90 days of scheduled implant procedure
10. Patients with pulmonary artery systolic pressure >70 mmHg via transthoracic echocardiography or alternative standard modality (e.g., direct pressure measurement) within 90 days
11. Concomitant clinically significant valve (aortic, mitral, or pulmonic) disease requiring immediate (± 30 days of study procedure) repair or replacement
12. Active endocarditis or infection within 3 months of scheduled implant procedure
13. Cerebrovascular accident within 3 months of scheduled implant procedure
14. Non-cardiac disease limiting life expectancy to be less than 12 months at baseline evaluation
15. Documented history of bleeding diathesis, coagulopathy or gastrointestinal bleeding within 3 months of scheduled implant procedure
16. Evidence of right sided intracardiac mass, thrombus, or vegetation
17. Prior venous stent placed within the access route (e.g., sub-clavian vein) that could negatively react with device
18. Previously treated tricuspid valve which included implantation of a bioprosthetic valve or mechanical valve
19. Known hypersensitivity to cobalt chromium, nitinol or titanium
20. Known hypersensitivity to anticoagulation therapy or contrast agent, which cannot be adequately medicated

21. Patient is a current intravenous drug user
22. Female of child-bearing potential is pregnant or lactating
23. Patient is currently participating or has participated in another investigational drug or device clinical study within 30 days of study screening activity
24. Patient requires emergent/emergency treatment for tricuspid insufficiency
25. Patient is under guardianship

8 PROCEDURES AND METHODS

8.1 INFORMED CONSENT

As the study Sponsor, Edwards Lifesciences must approve any modifications to the Informed Consent Form prior to submission to the regional ethics investigational review board (REB), independent ethics committee (EC) and/or Competent Authority (as required). A sample Informed Consent Form is provided in Appendix A – Sample Informed Consent Form.

Once the patient's physician has determined the patient's eligibility for the study, the background of the proposed study, and the benefits and risks of the procedures and study will be explained to the patient. The patient must sign the institution's approved Informed Consent Form prior to participation. Failure to provide informed consent renders the patient ineligible for the study.

The consent form will be written in the native language of the patient and administered only by the Investigator or EC approved personnel who speak the native language of the patient. The Principal Investigator or delegated person administering the consent must sign and date the Informed Consent Form to indicate that the purpose, risks and benefits of the study were explained to the patient and that their signature was witnessed.

The Investigator will retain the original consent form, a copy will be filed in the patient's medical record, and a copy of the Informed Consent Form will be provided to the patient.

Informed consent MUST be obtained prior to any study related procedures. A patient will be considered a "subject" and "enrolled" when they have signed the informed consent form agreeing to participate in the study and have been deemed eligible for study participation by meeting the study criteria (Sections 7.2-7.3). Subjects who are consented to participate in the study but do not fulfill enrollment criteria, will be considered "screen failures" as described below (Section 8.2). Signed informed consent forms must be retained by the study site for verification during on-site monitoring visits.

8.2 SUBJECT ENROLLMENT

[figure not shown]
A Screening/Enrollment Log provided by the Sponsor, will be maintained at the study site to document the screening and enrollment of all subjects assessed for study participation. The screening of subjects qualifying for this study should be carried out in a sequential, prospective manner, such that all patients are offered the possibility of participating in

the study and are therefore, evaluated according to the selection criteria defined in this protocol (see Figure 16). If a subject assessed for study participation does NOT enter the study, the reason in form of a “screen failure” code will be recorded on the log to ensure that a subject selection bias has not been introduced in the study. These reasons may include but not limited to:

- Qualifying patient is not offered an opportunity to participate by Investigator
- Qualifying subject refuses to participate
- Potential subject fails the screening criteria

All subjects assessed for study participation that have signed the informed consent form will be at the point of provisional enrollment and entered on the screening log. All subjects assessed for study participation that have signed the informed consent form, deemed eligible for study participation by the Screening Committee and have met the study criteria, will be at the point of final enrollment and assigned a sequential subject ID number by the study sponsor. The subject ID number together with the subject initials (if applicable) shall be used to identify the subject on all study-related documents.

8.3 BASELINE EVALUATION

1. Informed consent will be obtained from all patients who have been determined to be eligible study candidates and agreed to participate in the study.
2. Medical History (includes 6-month prior heart failure hospitalization rate), Clinical Evaluation (includes vital signs, weight and height), Concomitant Medication and NYHA classification
3. Administration of Health Status Questionnaires (SF-12, KCCQ)
4. Administration of Six Minute Walk Test
5. Clinical Laboratory Tests -
 - a. The following lab tests shall be done within 30 days of the scheduled implant procedure:
 - i. Troponins and/or cardiac enzymes (CK-MB) - *MI within 30 days of the scheduled implant procedure is an exclusion from study participation*
 - b. The following lab tests shall be done ≤ 2 weeks before implant procedure:
 - i. Brain Natriuretic Peptide (BNP)
 - ii. CBC and platelet count
 - iii. Complete metabolic panel
 - iv. Liver panel
 - c. The following lab tests shall be done ≤ 48 hours before the implant procedure:
 - i. Estimated Glomerular Filtration Rate (eGFR) - *eGFR result of < 25 is an exclusion from study participation for patients not already receiving dialysis*
 - ii. β HCG for women who are not sterile or post-menopausal- *positive result is an exclusion from study participation.*
 - iii. PTT/aPTT or PT/INR
6. Standard 12-lead Electrocardiogram (ECG)
7. Comprehensive Echocardiograms (Transthoracic [TTE] and Transesophageal [TEE]), if required¹, (within 90 days of scheduled implant procedure) including but not limited to, annulus size, ventricular size, regurgitant assessment, jet location, mean PAP and LVEF. Analysis will be conducted by the Investigator and Sponsor to certify the subject is eligible for the study.
8. Computed Tomography (CT) (within 90² days of scheduled implant procedure), that captures the anatomy of the subclavian and axillary veins, superior vena cava,

¹ The primary purpose of the TEE is to confirm the ability to image the tricuspid valve and possible anchoring location during the index procedure as this is the method that is used intra-procedure. If the TTE can demonstrate that the imaging of the valve and possible anchoring location is adequate, the TEE requirement at the baseline evaluation may be waived.

² If a pre-existing CT within 6 months of the scheduled implant procedure captures all the required anatomy for necessary measurements and the anatomy has not changed, the baseline CT can be waived and is not required to be repeated.

tricuspid valve and sub-valvular structures/anatomy, right atrium and right ventricle. Analysis will be conducted by the Investigator and Sponsor/designee to certify the subject is eligible for the study.

9. Invasive Hemodynamic Monitoring/Right Heart Catheterization (within 45 days of scheduled implant procedure) that includes, but is not limited to, right atrial pressure (RAP) and pulmonary artery pressure (PAP) measurements.³

Baseline evaluation data to be collected will include but is not limited to the information listed in the following table.

Table 4 - Baseline Evaluation

General Information	Clinical Information	Laboratory Measurements

 • Inclusion/exclusion evaluation • Informed consent • Age • Gender • Height • Weight 	
 • Heart Team determination • Medical history (e.g., EuroSCORE) /prior cardiovascular interventions / surgeries • Vital signs (Blood pressure, heart rate) • Concomitant Medication • NYHA classification¹ • Echocardiographic measurements (TTE & TEE), tricuspid regurgitation & heart function • Computed Tomography (CT) • Invasive Hemodynamic Monitoring/Right Heart Catheterization including pressure measurements • ECG results • Six minute walk test (pre & post walk data & results) • KCCQ & SF-12 questionnaires 	
Within 30 days of procedure:
 
 • Date of blood draw • Troponin² and/or CK-MB² 
Within ≤ 2 weeks of procedure:
 
 • Date of blood draw • BNP • WBC • RBC • Hematocrit • Hemoglobin • Platelets • ALT/SGPT • AST/SGOT • Bilirubin • LDH • Sodium & potassium • Urea 
Within ≤ 48 hours of procedure:
 
 • eGFR³ • PTT/aPTT or PT/INR • βHCG, if applicable⁴

1. Classification of < NYHA II is an exclusion from study participation
2. MI within 30 days of the scheduled implant procedure is an exclusion from study participation
3. eGFR result of < 25 is an exclusion from study participation
4. A positive result is an exclusion from study participation

³ If the screening echo confirms the PAP meets the study criteria, the right heart catheterization/hemodynamic assessment at the baseline evaluation may be waived.

8.4 ANTIPLATELET / ANTICOAGULATION THERAPY

All subjects will receive aspirin (at least 75 - 100 mg daily) prior to implant procedure. Subjects on warfarin will be asked to discontinue use prior to implant procedure. See Table 5.

Heparin will be administered at procedure start. During the procedure, activated clotting time (ACT) will be monitored and recorded on source documentation. Heparin will be administered during the procedure as needed to maintain the subject's ACT at ≥ 250 sec. The sheaths may be removed when ACT level is appropriate (e.g., reaches < 150 sec) after implantation of the study devices.

Implanted subjects will receive aspirin (at least 75 - 100 mg daily) post implant procedure through the 6 month follow-up visit. Additionally, patients with pre-existing atrial fibrillation will continue with their prescribed blood thinning medication (e.g., Coumadin® or Jantoven®) (INR > 2.5) post implant procedure through the 6-month follow-up visit. For patients not in atrial fibrillation, a second antiplatelet medication of the investigator's choice (e.g., Plavix) shall be prescribed post implant procedure through the 6-month follow-up visit. The antiplatelet regimen past the 6-month follow-up visit will be determined at the Investigator's discretion.

Table 5 - Summary of Recommended Concomitant Medical Therapy

Medication	Pre-Procedure	Inter-Procedure	Post-Procedure	1 Month Follow-Up	6 Month Follow-Up
IV Heparin		X	X ⁴		
Aspirin 75-100 mg daily	X		X	X	X
Warfarin or alternative (AFib Patients)			X	X	X
Plavix or alternative (Non-AFib Patients)			X	X	X

NOTE: The Investigator will determine the antiplatelet/anticoagulation therapy for study subjects on an existing dual antiplatelet therapy or with known hypersensitivity to the required medications in Table 5.

⁴ As needed as a bridge to warfarin where applicable

8.5 DEVICE PREPARATION

A description of device preparation and use is provided in the Instructions for Uses (IFUs), (See Clinical Investigator's Brochure). Investigators must be familiar with the information described in the IFU prior to use of the FORMA System.

An Edwards Representative that has been trained on the preparation of the FORMA System will be in attendance at all implant procedures.

8.6 IMPLANT PROCEDURE

The implant procedure shall be performed under general anesthesia with hemodynamic monitoring in an operating room, catheterization lab or hybrid operating room with fluoroscopic and echocardiographic imaging capabilities. The use of cardiopulmonary bypass is not required.

The following study procedures will occur during the implant procedure:

1. Safety Evaluation
2. Transesophageal Echocardiogram
3. Angiographic Imaging
4. Invasive Hemodynamic Monitoring/Right Heart Catheterization including right atrial pressure measurements pre and post implant
5. Heparin administration to achieve (and maintain) an ACT of ≥ 250 during the implant procedure

Subjects will be monitored in the operating room as needed with special attention to hemodynamic condition and cardiac rhythm. Subsequent monitoring of subjects will be continued in the recovery room or ICU.

The date of the implant procedure will be considered as Day 0 for the purpose of determining specified time intervals for the follow-up visit for the implanted and non-implanted cohorts.

Procedure data to be collected will include but is not limited to the information listed in the following table.

**Table 6 - Procedure Information**

General Information	Clinical Information	Laboratory Measurements

 • Hospital admission date • Subject identification number • Names of Interventional Cardiologist & Access Management Physician • Procedure date • Access site • Timing of implant procedures • FORMA System identification & disposition 	
 • Fluoroscopy duration & contrast volume • Heparin administration & ACT levels • TEE measurements, tricuspid regurgitation & heart function • Angiographic Imaging • Invasive Hemodynamic Monitoring/Right Heart Catheterization and pressure measurements performed • Post-implant antiplatelet / anticoagulation regimen • Adverse events • Device malfunction 	
Within 24 hours post implant:
 
 • Troponin¹ and/or CK-MB¹

1. *If an elevation was noted post implant (within 24 hours), tests must be repeated three times or until not clinically significant*

8.6.1 ANTIBIOTIC PROPHYLAXIS

It is recommended that all recipients be prophylactically treated for endocarditis to minimize the possibility of infection.

8.6.2 CONTRAST MEDIA

Careful management of contrast media is required for these patients. Accurate measurement of the dye used during the implant procedure shall be captured in the appropriate case report form.

8.6.3 DISCHARGE

The following procedures will be performed prior to discharge from the hospital/unit:

1. Clinical Evaluation and Concomitant Medication
2. Safety Evaluation
2. Clinical Laboratory Tests
 - a. BNP
 - b. CBC and platelet count
 - c. Complete metabolic panel

- d. Liver panel
 - e. PTT/aPTT or PT/INR
 - f. eGFR
 - g. Troponins and/or cardiac enzymes (CK-MB), only required if an elevation was noted post implant (within 24 hours)
3. Standard 12-lead ECG
 4. Comprehensive Transthoracic Echocardiogram, including but not limited to, annulus size, ventricular size, regurgitant assessment and jet location

Discharge data to be collected will include but is not limited to the information listed in the following table.

Table 7 - Discharge Information

General Information	Clinical Information	Laboratory Measurements

 • Discharge date • Weight 	
 • Vital signs (Blood Pressure, Heart Rate) • NYHA classification • TTE measurements, tricuspid regurgitation & heart function • ECG results • Post-implant antiplatelet / anticoagulation regimen • Adverse events 	
 • Date of blood draw • Troponin and/or CK-MB, if applicable • BNP • WBC • RBC • Hematocrit • Hemoglobin • Platelets • ALT/SGPT • AST/SGOT • Bilirubin • LDH • Sodium & potassium • Urea • eGFR • PTT/aPTT or PT/INR

8.7 FOLLOW-UP VISITS

Follow-up visits will be conducted at 1 month, 6 months, and annually for 3 years post implant procedure intervals as illustrated in Table 9. The following procedures will be conducted during follow-up visits:

1. Clinical Evaluation, Concomitant Medication and NYHA classification
2. Administration of Health Status Questionnaires (e.g., SF-12, KCCQ)

3. Administration of Six Minute Walk Test
4. Safety Evaluation
5. Clinical Laboratory Tests :
 - a. BNP
 - b. CBC and platelet count
 - c. Complete metabolic panel
 - d. Liver panel
 - e. PTT/aPTT or PT/INR
 - f. eGFR
6. Standard 12-lead ECG
7. Comprehensive Transthoracic Echocardiogram, including but not limited to, annulus size, ventricular size, regurgitant assessment and jet location

Follow-up data to be collected will include but is not limited to the information listed in the following table.

Table 8 - Follow-Up Visit Information

General Information	Clinical Information	Laboratory Measurements

 • Visit date • Height • Weight 	
 • Vital signs (Blood Pressure, Heart Rate) • NYHA classification • TTE measurements, tricuspid regurgitation & heart function • ECG results • Six minute walk test (pre & post walk data & results) • KCCQ & SF-12 questionnaires • Concomitant Medication • Adverse events 	
 • Date of blood draw • BNP • WBC • RBC • Hematocrit • Hemoglobin • Platelets • ALT/SGPT • AST/SGOT • Bilirubin • LDH • Sodium & potassium • Urea • eGFR • PTT/aPTT or PT/INR

8.7.1 FOLLOW-UP VISIT WINDOWS

Post-procedure follow-up visits will be performed on all implanted study subjects at 1 month, 6 months, and annually for 3 years post implant procedure intervals as illustrated in Table 9 below:

**Table 9 - Follow-up Visit Windows**

Scheduled Follow-up Interval	Follow-up Window
1 month (30 days)	± 7 days
6 months (183 days)	± 30 days
Annually (365 days) up to 3 years	± 45 days

During the follow-up visits, medical information, findings and results will be entered in the appropriate electronic case report forms.

Study subjects who have signed the Informed Consent, are deemed eligible and considered enrolled in the study but do not have the study procedure (incision) occur will be exited from the study immediately.

Study subjects who have signed the Informed Consent, are enrolled in the study, have the study procedure (incision) occur but do not receive the investigational device will be classified as “non-implanted” study subjects and exit the study at the 6 month follow-up visit. Non-implanted study subjects must complete safety evaluations but, will be exempt from all other study follow-up visit procedures.

Table 10 - Summary of Required Study Procedures

STUDY PROCEDURES	BASELINE	IMPLANT PROCEDURE ¹ (Day 0)	DISCHARGE ²	1 MONTH (30 ± 7 days)	6 MONTHS (183 ± 30 days)	ANNUAL (for 3 yrs) (365 ± 45 days)
Informed Consent	X					
Medical History	X					
Clinical Evaluation	X		X	X	X	X
NYHA Class Assessment	X			X	X	X
Health Status Questionnaires	X			X	X	X
Six Minute Walk Test	X			X	X	X
Safety Evaluation		X	X	X	X	X
Brain Natriuretic Peptide (BNP)	X		X	X	X	X
CBC and Platelet Count	X		X	X	X	X
Complete Metabolic Panel	X		X	X	X	X
Liver Panel	X		X	X	X	X
PTT/aPTT or PT/INR	X		X	X	X	X
βHCG	X ³					
eGFR	X ⁴		X	X	X	X
Troponins and CK-MB	X	X ⁵	X ⁶			
ECG	X		X	X	X	X
Transesophageal Echocardiogram	X ⁷	X				
Transthoracic Echocardiogram	X		X	X	X	X
Pre-Implant Computed Tomography	X					
Angiographic Imaging		X				
Invasive Hemodynamic Monitoring/Rt Heart Cath.	X ⁸	X				

¹ Implant procedure must be scheduled within 90 days of the baseline transthoracic echocardiogram and 90 days of the pre-implant procedure computed tomography (CT). If a pre-existing CT within 6 months of the scheduled implant captures all the required anatomy for necessary measurements & the anatomy has not changed, the baseline CT can be waived & is not required to be repeated.

² Discharge from hospital/unit post implant procedure

³ βHCG for women who are not sterile or post-menopausal

⁴ eGFR result of < 25 is an exclusion from study participation

⁵ Test will be taken post-implant (within 24 hours). If an elevation is noted, test must be repeated three times or until not clinically significant.

⁶ If an elevation was noted post implant (within 24 hours), test must be repeated three times or until not clinically significant

⁷ The primary purpose of the TEE is to confirm the ability to image the tricuspid valve during the index procedure as this is the method that is used intra-procedure. If the TTE can demonstrate that the imaging of the valve is adequate, the TEE requirement at the baseline evaluation may be waived.

⁸ If the screening echo confirms the PAP meets the study criteria, the right heart catheterization/hemodynamic assessment at the baseline evaluation may be waived.

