8.10 SUBJECT STUDY COMPLETION

Study subjects complete and exit the study when no additional follow-up visits, procedures, or data collection are required. Patients will then continue to be followed by their primary health care provider as required.

A subject will also be exited from the study in the following instances:

- Subject signs informed consent form, is deemed eligible and considered enrolled but does not undergo the study procedure
- Subject undergoes study procedure and does not receive investigational device (will continue in study for safety evaluations only and exit the study at the 6 month follow-up visit)
- Implanted subject requires the investigational device to be explanted for any reason (will continue in study for safety evaluations only and exit the study at the 6 month follow-up visit)
- Subject is lost-to-follow-up
- Subject withdraws participation from the study or is withdrawn from the study
- Subject expiration

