13 STATISTICAL ANALYSIS

13.1 SAMPLE SIZE

The primary endpoint is all-cause mortality at 30-days. Survival probabilities and standard errors will be estimated using the Kaplan Meier method and Greenwood formula respectively.

A performance goal of 18% was pre-specified for the 30-day rate of all-cause mortality in TVR (Tricuspid Valve Regurgitation) subjects treated with the Edwards FORMA Tricuspid Transcatheter Repair System, which was based on review of literature and early clinical studies (reference Section 1.3). The hypothesis for the primary endpoint is as follows:

- $H_0: \pi \geq 18\%$
- $H_A: \pi < 18\%$

Where π represents the all-cause mortality rate at 30 days.

The study is powered to detect a clinically significant difference between the expected mortality of the treatment group and the 18% Performance Goal. Based on the initial experience of the device (with some additional uncertainty assumptions), the estimated true rate was established to be 7.5% or less. Targeting a clinically significant difference of 10.5% (absolute reduction of greater than 50%), a sample size of 63 subjects will yield

at least 80% power to detect this difference at a significant level of 0.05. With a proportion of up to 9 investigational centers utilizing a roll-in subject and with a potential dropout rate of approximately 10%, an enrollment target of 78 subjects will ensure a sample size of 63 is available for analysis.

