13.3 ANALYSIS POPULATION

The analysis population will be grouped into four analysis cohorts that in total comprise all subjects enrolled in this study. The analysis cohorts are defined below:

- Enrolled Cohort: all subjects enrolled in the study
- As Treated (AT) Cohort: all subjects who are enrolled and undergo the study procedure (chest incision)
- Implanted Cohort: all subjects who undergo the study procedure (chest incision), receive and retain the investigational device upon leaving the procedure room
- Roll-In Cohort: first subject enrolled and treated at a center that does not have previous device or procedure experience and is classified as a “roll-in” subject

The primary endpoint will be reported based on the AT cohort. For the secondary endpoints and clinical outcomes, technical success analysis will be performed for the AT cohort, while device success, procedure success and clinical outcomes analyses will be performed for the implanted cohort. Roll-In subjects will be analyzed separately. Subject listings for adverse events, deaths will include all enrolled subjects.

For subjects with major protocol violations, which include but are not limited to study criteria and informed consent violations, a secondary analysis will be conducted in which those subjects will be excluded from the implanted cohort analyses.

Further analysis plans will be outlined in the statistical analysis plan.

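### The as-treated cohort starts at chest incision, so a death after induction or procedural TEE but before incision is outside the tested 30-day mortality, and a subject aborted at that stage has no 30-day status check

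*Protocol*

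**What the plan says.** **Endpoint and cohort.** The trial has one hypothesis test. Protocol 13.1 states: "A performance goal of 18% was pre-specified for the 30-day rate of all-cause mortality". Protocol 13.3 states: "The primary endpoint will be reported based on the AT cohort". It defines that cohort as "As Treated (AT) Cohort: all subjects who are enrolled and undergo the study procedure (chest incision" (closing bracket cut), and SAP 2.4 repeats the definition.

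**Exit.** Protocol 8.7.1, below Table 9, says that enrolled subjects who "do not have the study procedure (incision) occur will be exited from the study immediately". Protocol 8.10 lists the same exit: "Subject signs informed consent form, is deemed eligible and considered enrolled but does not undergo the study procedure". No safety follow-up is attached to that item. The next two items, for subjects who had the procedure without receiving a device and for explanted subjects, do provide safety evaluations up to the 6-month visit.

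**Content of the procedure.** Protocol 8.6: "The implant procedure shall be performed under general anesthesia with hemodynamic monitoring". The same section lists TEE, invasive hemodynamic measurements before and after implant, and heparin as parts of the implant procedure. Protocol 8.4: "Heparin will be administered at procedure start". Protocol 3.1 names death among the risks of the overall procedure, and there counts the use of anesthesia as part of it.

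**Listings.** Protocol 13.3: "Subject listings for adverse events, deaths will include all enrolled subjects".

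**The concern.** The protocol treats anesthesia as procedure risk, but the count for the tested endpoint begins later, at the incision. A subject who arrests at induction, or is fatally injured by the procedural TEE, is enrolled and has been exposed to study-mandated steps, yet contributes to neither the numerator nor the denominator of the primary proportion.

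The second gap is follow-up. Protocol 8.3 allows the baseline TEE and the baseline right heart catheterization to be waived under stated conditions. For some subjects the first TEE or invasive measurement therefore takes place on the table, where a decision to abort is plausible. Someone aborted after induction but before incision leaves the study at once, without the safety evaluations given to an incised subject who receives no device. Day 0 in 8.6 is also tied to the implanted and non-implanted cohorts, so this subject has no defined time origin.

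At stake is whether a single-arm mortality claim, meant to support regulatory approval (section 2), covers the whole procedure. No sensitivity analysis of the primary endpoint in the Enrolled cohort is planned.

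**Working it through.** **1. The plan's own figure.** Inputs from protocol 13.1: goal 18%, assumed true rate 7.5%, alpha 0.05, power at least 80%, n = 63. With an exact one-sided binomial test at n = 63, success means at most 6 deaths. P(X ≤ 6 | 18%) = 0.0487 and P(X ≤ 6 | 7.5%) = 0.808. The figure of 63 reproduces, and nothing below changes it.

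**2. The protocol's decision rule.** Protocol 13.4 and SAP 3.2 require the one-sided 95% upper limit (Kaplan-Meier with Greenwood standard error) to be below 0.18. With complete 30-day status this limit is p + 1.645 × √(p(1 − p)/n).

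| Deaths / n | p | Upper limit | Result |
|---|---|---|---|
| 6/63 | 9.5% | 15.6% | pass |
| 7/63 | 11.1% | 17.6% | pass |
| 8/63 | 12.7% | 19.6% | fail |
| 7/64 | 10.9% | 17.4% | pass |
| 8/64 | 12.5% | 19.3% | fail |

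For 7/63: 0.1111 + 1.645 × √(0.1111 × 0.8889/63) = 0.176. For 8/64: 0.125 + 1.645 × √(0.125 × 0.875/64) = 0.193.

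Adding one pre-incision death reverses the result when the AT cohort has exactly 7 deaths in 63. With 6 it does not (7/64 passes).

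**3. How likely the boundary is.** At 7.5%, P(X ≤ 7) = 0.902 and P(X ≤ 6) = 0.808, so P(X = 7) = 0.094. The expected number of deaths is 63 × 0.075 = 4.7.

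**4. The opposite direction.** Adding aborted survivors enlarges the denominator. Starting from 8/63 (fail), 8/68 has upper limit 18.2% and 8/69 has 17.9%. It would take 6 added survivors to turn that failure into a pass, so per subject this effect is much weaker than that of a death.

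**5. Effect on false success, under an assumption.** The documents give no pre-incision death rate r, so take r = 0.5% to 3%. Suppose mortality counted from induction is exactly 18%. Mortality among incised subjects is then (0.18 − r)/(1 − r). The last column is P(X ≤ 7) at n = 63.

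| r (assumed) | AT mortality | P(success) under the protocol's rule |
|---|---|---|
| 0 | 18.0% | 9.9% |
| 0.5% | 17.6% | 11.4% |
| 1% | 17.2% | 13.1% |
| 2% | 16.3% | 17.2% |
| 3% | 15.5% | 22.2% |

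The starting value of 9.9%, rather than 5%, comes from the approximate limit and is a separate matter. The part due to the cohort rule is the increase over 9.9%: about 1.5 points at r = 0.5% and about 12 at r = 3%.

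**The case against.** The strongest reply is that the cohort rule is explicit, identical in both documents, and a legitimate design choice. Much of that stands, and it rules out several stronger readings that a reader might infer.

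- **That such a death would go unrecorded.** It would not. Safety evaluation and adverse events are part of the procedure record (8.6, Table 6). SAEs go to the sponsor within 24 hours, and adverse events are followed until resolved or explained (12.1). The DMC monitors SAEs (section 15), and listings cover all enrolled subjects. The death is missing from the tested proportion, not from the study. The follow-to-resolution rule also gives some cover to an aborted subject who already had an adverse event. It does not provide a scheduled 30-day status check.
- **That the bias can only favor the device.** Omitted deaths do. Omitted aborted survivors act the other way, though weakly.
- **That heparin and line placement come before the incision.** The documents do not give the order. Protocol 8.4 puts heparin at procedure start, which may coincide with or follow the incision. General anesthesia and TEE are the clear cases.
- **That puncture access could leave treated subjects outside the cohort.** SAP 4.1.3 plans to summarize time from skin incision to closure, so an incision is an expected step, and device and delivery details are redacted.
- **That the comparison with 18% is shown to be biased.** This depends on when the cited surgical series began counting, which protocol 1.3 does not say.

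The reply does not put a death at induction back into the primary endpoint, and it gives an aborted survivor no 30-day status.

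**Conclusion.** The point holds in limited form. As written, a death after induction or procedural TEE but before incision is excluded from the tested 30-day mortality, and a subject aborted at that stage who leaves alive has no scheduled status check at 30 days.

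The likely effect is small. One such death decides the test only if the AT cohort has exactly 7 deaths in 63, which has probability 9.4% at the planned rate, and a pre-incision death must also occur. This rests on complete 30-day status and 63 analyzed subjects. The false-success figures rest on an assumed pre-incision death rate that the documents neither give nor bound. The net direction depends on the unknown mix of pre-incision deaths and aborted survivors. It is a gap worth closing because closing it is cheap, not evidence that the planned test is invalid.

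**What to change.** 1. In protocol 13.3 and SAP 2.4, define the AT cohort as enrolled, non-roll-in subjects in whom the procedure is started: induction of anesthesia or the first invasive step in the procedure room, whichever is earlier. Make that date Day 0 in 8.6.
2. In 8.7.1 and 8.10, limit immediate exit to subjects who never start. Give those started but not incised the same safety follow-up as non-implanted subjects, at minimum vital status at 30 days. This must accompany step 1: without status, an aborted survivor is censored at about Day 0 and adds almost nothing to the Kaplan-Meier estimate.
3. Count started-but-not-incised subjects as Technical Success failures.
4. Use one term for the start of the procedure. At present 8.7.1 uses incision and 13.3 uses chest incision, while implant procedure means the whole session in 8.6 but placement of the device in section 19.

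Cost: wording in these sections and a few extra safety contacts. The Technical Success rate may fall, and the mortality estimate may move slightly in either direction. The sample size of 63 is unchanged.
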